Randomized subjects will receive 8 days of study medication at the time of randomization. A riboflavin tracer (50mg) will be added to each capsule to serve as an objective measure of medication adherence on the day of the alcohol challenge⁵⁶. Two bottles will be dispensed to each subject: 1) 11 pills of Lacosamide or placebo over-encapsulated with 50mg of riboflavin and 2) 3 Pills of lacosamide or placebo over-encapsulated with 50mg of riboflavin. Subjects will take 100 mg of lacosamide (or placebo) twice per day until day 7. On day 7 subjects will increase to 150mg twice daily. Based on the metabolism of this drug, we expect to be within range of 90% of steady state for a 300 mg daily lacosamide dose by day 8 when the alcohol challenge trial will occur which is consistent with the clinical dose range (300-400mg daily as monotherapy) of this drug when it is used for seizure disorders⁵⁷. Subjects who are not able to achieve the target dose due to adverse effects will be discontinued from the study.

								Self-
Dose	Day 1	Day 2	Day 3	Day 4	Day 5	Day 6	Day 7	Admin
AM		100mg	100mg	100mg	100mg	100mg	150mg	150mg
PM	100mg	100mg	100mg	100mg	100mg	100mg	150mg	

The seven-day period of medication titration will begin within a window of 6 days depending upon scheduling the alcohol challenge. Subjects may be randomized and instructed to start the medication up to 6 days later so that day 8 will conicide with the alcohol challenge appointment. Subjects will be given a brief phone reminder to start medication on Day 1. During the sevenday period of medication titration, subjects will be asked to answer a medication compliance question each day by smartphone using the REDCap data capture through a web-based portal⁵⁸. In addition to assessing medication compliance, subjects will also be asked to rate their craving for alcohol each day using the alcohol VAS. Subjects will receive a \$5 reimbursement on each day they complete the VAS and answer the medication compliance question using the REDcap web-based portal. Subjects will be contacted by telephone on day 3 of the medication titration period for an adverse event assessment.

Medication Visit #2

After the 7-10 day washout period subjects will return to the lab to receive study medication prior to the alcohol challenge #2. Subjects will complete the same tests and interviews completed during the randomization visit (See appendix A for schedule of events). Based on the assessments at medication visit #2, subjects be discontinued for the following reasons: pregnancy, recreational drug use, evidence of non-compliance with study medication, suicidal thoughts or behavior, and use of a new medication that would make participation unsafe. Subjects will receive an 8-day supply of study medication and will be scheduled for the alcohol challenge #2.

Alcohol Challenge Trials 1 & 2: Subjects will return to the laboratory on day 8 of titration for each medication trial to complete the alcohol challenge. For safety reasons, subjects will be asked to arrange transportation plans (no driving) prior each of the alcohol challenge trials.

There will be a 7-10 day washout period between alcohol challenge Trial 1 and medication visit 2. Based on the known half-life of lacosamide, all of the medication will be cleared within 7 days. The washout may extend to 10 days to accommodate the scheduling of Trial 2. Concomitant medications, urine drug screening, urine pregnancy testing, blood alcohol level will be assessed to determine eligibility to proceed with the challenge. Blood alcohol level must be 0.000 to continue with the study procedures. Urine collected for drug screening will be exposed to ultraviolet light as an objective test of medication compliance. If no fluorescence is observed in the urine sample the subject will be excluded from continuing with the challenge. Measures of drinking (TLFB), cravings, (OCDS and AUQ), and neurocognitive function (COWAT, WMSIII Spatial Span and Digit Span tests) will be collected to inform secondary outcomes. Subjects will be observed taking the morning dose of lacosamide (or placebo) on the day of the challenge (after compliance is confirmed via a urine screening). The peak plasma concentration of lacosamide should be reached approximately 60 minutes after administration. The alcohol self-administration session will begin no sooner than one hour after the administration of the observed 150mg morning dose. The alcohol self-administration will be conducted in the GCRU. The room will be a carpeted and furnished with a lounge chair, side table and television which allows access to popular streaming entertainment (e.g., Netflix, YouTube). A small unobtrusive camera is mounted in one corner to allow for monitoring without study staff being present in the room. The room has ready access to a bathroom. The alcohol self-administration is divided into four segments: 1) a 5-minute segment for the priming dose, 2) a 40-minute segment for observing alcohol's effects, 3) a 60-minute segment of alcohol self-administration (Block1) and, 4) a second 60-minute segment of alcohol self-administration (Block2) [see figure 2 for the alcohol self-administration Procedure].

Priming dose. Subjects will be given a priming drink designed to increase the subject's blood alcohol level (BAL) to 0.03g/dl, using the alcohol of their choice that is 24% Alcohol By Volume (ABV) or greater. The volume of alcohol will be calculated using an online

Figure 2: Alcohol Self-Administration Procedure								
Priming Dose 5 minutes Drink mixed to achieve BAL= 0.03g/dl	5 minutes Drink mixed to achieve BAL= 40 minutes Craving and intoxication 40 minutes 60 minutes each 4 drinks per block							

tool developed by UW-Madison (http://dionysus.psych.wisc.edu/WebCMS/baccalc.htm) based on a formula described by Watson⁵⁹ The subjects will be asked to drink the priming drink over a period of 5 minutes. Part of the purpose of the priming drink is to normalize drinking in the laboratory.

Observation period. Subjects will be observed for 40 minutes following the priming dose of alcohol to allow for absorption of the alcohol.

Alcohol self administration Blocks 1 and 2. In each of the alcohol self-administration Blocks, subjects will be presented with four drinks, each mixed to raise their BAL 0.015g/dl. They will be told that they can either consume the desired number of drinks over the following 60 minutes or they will receive the equivalent dollar amount of the cost of each drink (\$3.00) they did not consume before leaving the clinic. At the end of each 1 hour session the tray with the remaining drinks will be removed and the amount of alcohol remaining will be measured. Cravings will be

assessed using the AUQ and VAS every 30 min during the self-administration blocks. Based on the rate of alcohol metabolism over the time of the trial, we anticipate that subjects who consumed every drink could reach a BAC of .09 to .13 g/dl depending upon differences in alcohol metabolism. Safety assessments will be completed (intoxication, sedation, adverse effects) prior to subjects leaving the laboratory. Subjects will be required to have a plan for transportation home that does not involve driving. Subjects will not be released until their blood alcohol level is ≤ 0.04 g/dl and they are not behaviorally impaired. After the second alcohol self-administration trial has been completed subjects will receive a copy of the NIAAA publication *Rethinking Drinking*⁶⁰ and will be encouraged to review rethinking drinking materials online.

Subject compensation

Subjects will be compensated up to \$418 for completion of all study activities. Subjects will receive a reimbursement of \$40 for the screening visit, \$20 for the randomization visit and \$20 for the assessment visit prior to Trial 2. Subjects will receive \$80 for each of the two alcohol challenge trials and a \$40 completion bonus if they complete both challenges. Subjects will receive a \$5 payment each on day during the two 7-day titration periods that they respond to the REDcap survey to rate their alcohol craving and report their medication compliance. Subjects will also receive a \$10 completion bonus if they complete the craving scale and medication log on all seven days. Subjects may receive up to \$48 dollars in payments for drinks not consumed during the two alcohol self-administration Trials.

In addition to this \$418 of compensation, subject may also be reimbursed up to an additional \$60 for distributing study recruitment materials to other people who may want to take part in this study. Distributing recruitment materials is completely optional. subjects may take part in the study and decline to hand out flyers to people they know.

Subjects who report no recreational drug use other than marijuana at the time of phone screening but then test positive for recreational drug use other than marijuana at the first in-clinic visit will not be reimbursed. Subjects will be informed of this policy at the time of telephone screening. This measure is in place to prevent subjects from lying about no recreational drug use in order to receive compensation for a single visit in this study.

10 Assessment of Safety and Data Safety Monitoring Plan (DSMP)

10.1 Definitions

The following definitions will be used in the assessment of safety:

Adverse Event (AE) is any untoward or unfavorable medical occurrence in a human subject, including any abnormal sign (for example, abnormal physical exam or laboratory finding), symptom, or disease, temporally associated with the subject's participation in the research, whether or not considered related to the subject's participation in the research.

Serious Adverse Event (SAE) is any adverse event that (1) results in death;

- (2) is life-threatening;
- (3) results in inpatient hospitalization or prolongation of existing hospitalization;
- (4) results in a persistent or significant disability/incapacity;
- (5) results in a congenital anomaly/birth defect; or
- (6) based upon appropriate medical judgment, may jeopardize the subject's health and may require medical or surgical intervention to prevent one of the other outcomes listed in this definition (examples of such events include allergic bronchospasm requiring intensive treatment in the emergency room or at home, blood dyscrasias or convulsions that do not result in inpatient hospitalization, or the development of drug dependency or drug abuse).

Life-threatening means that the event places the subject at immediate risk of death from the event as it occurred.

Unanticipated Problem is defined as an event, experience or outcome that meets **all three** of the following criteria:

- is unexpected; AND
- is related or possibly related to participation in the research; AND
- suggests that the research places subjects or others at a greater risk of harm (including physical, psychological, economic, or social harm) than was previously known or recognized.

Possibly related means there is a reasonable possibility that the incident, experience, or outcome may have been caused by the procedures involved in the research

Unexpected means the nature, severity, or frequency of the event is not consistent with either:

- the known or foreseeable risk of adverse events associated with the procedures involved in the research that are described in (a) the protocol—related documents, such as the IRB-approved research protocol, any applicable investigator brochure, and the current IRB-approved informed consent document, and (b) other relevant sources of information, such as product labeling and package inserts; or
- the expected natural progression of any underlying disease, disorder, or condition of the subject(s) experiencing the adverse event and the subject's predisposing risk factor profile for the adverse event.

10.2 Safety Review

Both the risks listed in Section 6.1 and unknown risks will be monitored as follows:

Adverse events will be monitored from the time of study enrollment until the end of participation. Adverse events will be monitored by medical staff using the "adverse events" CRF. Adverse event monitoring will be conducted at a mid-week call during both titration periods. Adverse events will also be assessed on the alcohol self-administration challenge days. Subjects will be given a wallet card with a 24/7 telephone number in the event that there are adverse effects which the subject would like to consult with medical staff prior to the next scheduled visit. Adverse events will be assessed if at any point in the study a subject uses this

24/7 emergency phone contact. If a subject has an ongoing SAE or unanticipated problem at the time that the subject completes all study procedures, Adverse Event assessment will continue until satisfactory resolution (either resolved or stabilized and is not expected to resolve in the near term) of the event or problem.

For each recorded AE or SAE, the study MD staff or study nurse will assess expectedness based on the known published side effect profile for lacosamide. The study MD staff or study nurse will also assess severity based on the following criteria:

Mild: An event that is usually transient, requiring no special treatment, and does

not generally interfere with the subject's daily activities.

Moderate: An event that interferes with usual activities of daily living, causing

discomfort but poses no significant or permanent risk of harm to the subject. The event is usually ameliorated with additional specific

therapeutic intervention.

Severe: An event that interrupts usual activities of daily living or significantly

affects clinical status. The event poses a significant risk of harm to the subject and hospitalization may be required, and typically requires

intensive therapeutic intervention.

Life-threatening An event that puts the subject into imminent risk of death without intervention.

The study MD staff or study nurse will assess AE/SAE relationship to the investigational product based on the following criteria:

Unrelated: The subject did not receive the investigational product, the temporal sequence

of the AE/SAE onset relative to administration of the investigational product

is not reasonable, or there is another obvious cause of the AE/SAE.

Unlikely: There is evidence of exposure to the investigational product or there is

another more likely cause of the AE/SAE.

Possible: There is evidence of exposure to the investigational product, the temporal

sequence of the AE/SAE onset relative to administration of the investigational product is reasonable, but the AE/SAE could have been due to another equally

likely cause.

Probable: There is evidence of exposure to the investigational product, the temporal

sequence of the AE/SAE onset relative to administration of the investigational

product is reasonable, and the AE/SAE is more likely explained by the

investigational product than by any other cause.

Definite There is evidence of exposure to the investigational product, the temporal

sequence of the AE/SAE onset relative to administration of the investigational

product is reasonable, the AE/SAE is more likely explained by the

investigational product than by any other cause, and the AE/SAE shows a pattern consistent with previous knowledge of the investigational product or

investigational product class.

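### No adverse-event contact is scheduled after Trial 2, so late events after lacosamide are actively asked about in only one of the two sequences

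*Combined protocol and SAP*

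**What the plan says.** Section 10.2 introduces its plan with "Both the risks listed in Section 6.1 and unknown risks will be monitored as follows" and sets the window: "Adverse events will be monitored from the time of study enrollment until the end of participation". The scheduled contacts it names are one mid-week call in each titration period and an assessment on each challenge day. Appendix A marks AEs at all five visits; its last column is Trial 2, and no visit or call follows.

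One provision carries assessment past completion. It begins "If a subject has an ongoing SAE or unanticipated problem at the time that the subject completes all study procedures" and continues until the event resolves or stabilises. It applies to events already present, not to new ones.

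The other routes start with the subject:
- Section 6.1 opens with a general instruction to contact staff about health changes once medication has begun, with a wallet card and a 24/7 number. It has no end date.
- The DRESS paragraph of 6.1 asks subjects to contact a physician at once for rash, fever and other signs. It also has no end date.
- The Stevens-Johnson paragraph asks the same for the time on study medication.
- In 10.2, "Adverse events will be assessed if at any point in the study a subject uses this" telephone line.

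Section 9 supplies the timing. "The alcohol self-administration session will begin no sooner than one hour after the administration of the observed 150mg morning dose". "Safety assessments will be completed (intoxication, sedation, adverse effects) prior to subjects leaving the laboratory". "There will be a 7-10 day washout period between alcohol challenge Trial 1 and medication visit 2". The reason given for that interval is "Based on the known half-life of lacosamide, all of the medication will be cleared within 7 days".

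**The concern.** In a two-period crossover, ending AE capture at the last session treats the two sequences differently. A subject who takes lacosamide first is still in the study through washout and the placebo period, and is asked about AEs several times after stopping the drug. A subject who takes it second leaves scheduled follow-up on the day of the last dose. Whether a late lacosamide event is actively sought therefore depends on the sequence to which the subject was randomized, and the protocol gives no reason for the difference.

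At stake are subject safety and even AE ascertainment. A new event after Trial 2 reaches the AE summary for continuing review (10.3), or could count toward the enrolment-suspension rule for serious events (10.4), only if the team hears of it. The alcohol and craving outcomes are measured by the end of Trial 2 and are not affected.

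**Working it through.** **1. The plan's own duration.** Inputs from Section 9 and Figure 1: up to 14 days from baseline to randomization, a start window of up to 6 days, 7 days to the first challenge, a washout of up to 10 days, 7 days to the second challenge.

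14 + 6 + 7 + 10 + 7 = 44 days.

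This reproduces the stated maximum of 44 days. It ends on Trial 2 and leaves no day for follow-up.

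**2. The day of the last capsule.** From the dosing table in Section 8: 100 mg capsules 1 + 2×5 = 11; 150 mg capsules 2 + 1 = 3. These match the two dispensed bottles. The 14th capsule is the observed morning dose on day 8, the challenge day.

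**3. The same-day check.** Shortest time from that dose to the end of a completed session: 60 (dose to session) + 5 (priming) + 40 (observation) + 60 + 60 (two blocks) = 225 minutes = 3.75 hours. Other release conditions can only lengthen this. The check covers acute effects.

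**4. Scheduled AE contacts after the day of the last lacosamide dose (completers).** The mid-week call is placed on titration day 3 in Section 9 (2 days after the dispensing visit if dosing starts that evening) and 3–4 days after starting medication in Appendix A.

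| Contact | Lacosamide first: days after last lacosamide dose | Lacosamide second |
|---|---|---|
| Dispensing visit | 7 to 10 | none |
| Mid-week call, period 2 | 7 + 2 = 9 to 10 + 4 = 14 | none |
| Trial 2 | 7 + 7 = 14 to 10 + 7 = 17 | day 0 (dosing day) |
| Number after the dosing day | 3 | 0 |

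If the 6-day start window is assumed to apply in period 2 as well, the last lacosamide-first contact could fall at 17 + 6 = 23 days. Section 9 describes that window in terms of randomization, and 44 days has room for it only once, so 14 to 17 days is the figure to use.

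**5. Size.** Section 6.1 reports one delayed multi-organ hypersensitivity case among 4011 exposed subjects, 10 days after stopping. Equal allocation is assumed.

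- Protocol Summary, 112 subjects, 56 lacosamide second: 56 / 4011 = 0.014 expected; chance of at least one 1 − (1 − 1/4011)^56 = 1.4%.
- Section 12.2, 28 subjects, 14 lacosamide second: 14 / 4011 = 0.003 expected.
- Counting the three other possible cases in 6.1, whose timing is not given: 56 × 4 / 4011 = 0.056 expected; chance of at least one 5.4%.

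The documents give no basis for the chance that such an event would go unreported.

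**The case against.** The plan has more cover than the visit schedule shows. The general instruction in 6.1 has no end date and is not tied to one reaction. The DRESS advice is also open-ended and already names rash and fever, so little follows from the narrower Stevens-Johnson wording. Reporting deadlines for unanticipated problems in 10.3 run from when the investigator learns of the event, with no cut-off at the end of participation. Common dose-related effects should be caught at the mid-week call and the Trial 2 check. The later contacts in the lacosamide-first sequence are by-products of period 2, not designed drug follow-up. The day-14 call would come after a reaction timed like the 10-day case.

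All of that stands, and it rules out two stronger readings that a reader might infer:

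- *That subjects finishing on lacosamide have no safety cover after Trial 2, or that 10.2 contradicts 6.1.* The open-ended instructions in 6.1 say otherwise. The consent form and wallet card are also absent from the available copy and may add to them.
- *That the plan breaches its own 7-day or 10-day follow-up standard.* It sets none. The 7 days justify the crossover washout, and the 10 days describe a single case. Both are context only.

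The objection does not supply a scheduled contact. Every route to a new event after Trial 2 in the available text starts with the subject recognising a problem and calling.

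**Conclusion.** The point holds as a statement about scheduled contact: none after the dosing day for lacosamide-second completers, three for lacosamide-first completers, the last at 14 to 17 days. Active ascertainment of late lacosamide events is therefore uneven between sequences.

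Severity is low. The one delayed reaction with a stated timing is rare, with about 0.003 to 0.014 events expected in the lacosamide-second group across the two sample sizes in the document. This assumes equal allocation and that the 1 in 4011 rate carries over to this dose and duration. The conclusion covers only completers and the contacts in Section 10.2 and Appendix A. It is a cheap improvement to an otherwise workable safety plan.

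**What to change.** In Section 10.2 and Appendix A, extend the AE window with one telephone AE contact about 14 days after Trial 2. Make it for every subject in both sequences, so that the call does not reveal treatment order. Day 14 matches the minimum lacosamide-first follow-up. State in 10.2 that the 24/7 line and symptom-triggered contact run at least until that call, without shortening the open-ended advice in 6.1.

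The cost is one short call per subject (28 to 112 calls) by staff who already make the mid-week calls, a stated maximum participation of about 44 + 14 = 58 days, and a minor amendment for the IRB. The call mainly records events and evens out AE capture; subject-initiated contact remains the route to prompt care.

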10.3 Reporting Plans

The Principal Investigator at BMC/BU Medical Campus will report Unanticipated Problems, safety monitors' reports, and Adverse Events to the BMC/BU Medical Center IRB in accordance with IRB policies:

- Unanticipated Problems occurring at BMC/BU Medical Campus involving a fatal or lifethreatening event will be reported to the IRB within 2 days of the investigator learning of the event.
- Unanticipated Problems occurring at BMC/BU Medical Campus not involving a fatal or life-threatening event will be reported to the IRB within 7 days of the investigator learning of the event.
- Reports from safety monitors with recommended changes will be reported to the IRB within 7 days of the investigator receiving the report.
- Adverse Events (including Serious Adverse Events) will be reported in summary at the time of continuing review, along with a statement that the pattern of adverse events, in total, does not suggest that the research places subjects or others at a greater risk of harm than was previously known.
- Reports from safety monitors with no recommended changes will be reported to the IRB at the time of continuing review.

